## 8. Statistical analysis plan and sample size calculation

**Statistical analysis plan.** The primary statistical analysis is designed as intention-to-treat with the use of two-tailed Fisher's exact test to compare the primary endpoint between two groups. The primary endpoint will be reported as an absolute number, percentage, and relative risk with 95% CI. Secondary statistical analysis of the primary endpoint will be made using an unadjusted Cox proportional-hazards model. The data will be censored on the time of VTE registration, or death, or discharge from the hospital and reported as a hazard ration with 95% CI. Kaplan-Meier curves will be used to compare time-to-event distribution. Cox proportional-hazards models adjusted for the clinical center, surgery profile, type of surgery, emergency of surgery, type of anesthesia, surgical radicalism, malignant disorder, Caprini score, and time to start LMWH injections will be used.

A similar analysis for the per-protocol population, but that excluded patients with gross violations of the protocol and premature discontinuation of at least one component of combined prophylaxis (ECS, IPC or LMWH), will be performed for the primary endpoint.

Secondary endpoints will be analyzed with two-tailed Fisher's exact test and will be represented as an absolute number, percentage, and relative risk with 95% CI.

Cox proportional-hazards models will be used for the prespecified subgroup analysis for the following subgroups: surgical profile; type of surgery; the urgency of surgery; the radicalism of surgery; type of anesthesia; malignant or benign disorder; preoperative, postoperative, or delayed start of LMWH injections; and pre-operative or post-operative IPC application.

Sensitivity analysis will address to the per-protocol analysis, compliance with IPC (restricted for 90% and more), duration of follow-up (restricted to 7 days and more), and the number of postoperative DUS (restricted with two and more).

Missing data on the primary endpoint are not anticipated in the inpatient settings, so no analysis for missing data being planned.

Adjusting for multiple comparisons and imputation for missing values will not be performed. The 95% confidence intervals will be not adjusted for multiplicity, and therefore, inferences drawn from these intervals might be not reproducible. The interim analysis is not planned.

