**Sample size calculation.** The prevalence of asymptomatic postoperative vein thrombosis at the top of standard prophylaxis with ECS and LMWH was assumed as 30% based on our previous observations involving patients at high and extremely high risk. Taking into account the fact that pharmaco-mechanical prophylaxis should provide a further 60% VTE risk reduction, the absolute difference of 18% is assumed. Using Fisher's exact test for primary statistic analysis, with a power of 80% and type I error of 0.05, the sample size is estimated as 180 subjects (90+90 in each group). Assuming 10% withdrawal due to the protocol deviations, patient's decision, or incomplete data, the sample size is calculated as 200 subjects. Considering prespecified subgroup analysis for the patients with an early and delayed start of LMWH, we decided to double the sample size to achieve sufficient power for separate analyses of the suggested subgroups. IBM SPSS will be used for data processing.

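### No treatment-by-subgroup interaction test is planned, so any claim that IPC works in one subgroup but not another would rest on comparing separate results

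*Combined protocol and SAP*

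**What the plan says.** Section 8 (Statistical analysis plan) states that "Cox proportional-hazards models will be used for the prespecified subgroup analysis for the following subgroups" and lists eight factors. They cover the surgical procedure, anesthesia, malignancy, timing of the first LMWH injection in three levels (before surgery, after surgery, delayed), and whether IPC began before or after surgery. Section 2 lists the same factors as secondary objectives. Neither section names an interaction term, a heterogeneity test or any other comparison between subgroups.

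The sample size paragraph of section 8 deals with one factor only, early versus delayed LMWH start, and says "we decided to double the sample size to achieve sufficient power for separate analyses of the suggested subgroups". The base calculation being doubled is "with a power of 80% and type I error of 0.05, the sample size is estimated as 180 subjects (90+90 in each group" subjects), which becomes 200 after a 10% allowance for withdrawal.

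Section 8 also says that no multiplicity adjustment will be made and warns that conclusions drawn from the unadjusted intervals may not be reproducible.

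**The concern.** Whether IPC works differently with early and with delayed LMWH is a question about the difference between two effects. Two separate tests do not answer it. When each subgroup has power of about 80–90%, it is quite likely that one reaches p<0.05 and the other does not, even if the true effect is identical in both.

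Half of the enrolment is justified by this subgroup question. If the results are read subgroup by subgroup, a statement that IPC helps with one LMWH timing and not the other could be a chance finding, and it could influence who is offered IPC.

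**Working it through.** **Inputs (section 8).**
- Control risk: "at the top of standard prophylaxis with ECS and LMWH was assumed as 30"%.
- Effect: "the absolute difference of 18% is assumed", so 30% versus 12%.
- Primary test: "two-tailed Fisher's exact test to compare the primary endpoint between two groups".
- Alpha 0.05, power 80%, 90 per group.
- Total after doubling: 2 × 200 = 400 enrolled (derived, not printed). After 10% withdrawal, 400 × 0.9 = 360 evaluable.
- Subgroup shares: not given. All splits below are assumptions.

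**The plan's own figure.** The two-proportion formula for 30% versus 12% gives 80 per group without continuity correction and 90 with it, which matches the plan. Exact two-sided Fisher power at 90 per group is 81.2%. Withdrawal: 180/0.9 = 200. The sample size is reproduced and is not in dispute.

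**Chance that exactly one of two subgroups is significant, same true effect in both.** With subgroup powers A and B this is A(1−B) + B(1−A). At the nominal 80% it is 2 × 0.8 × 0.2 = 32%.

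Fisher, 50:50:
- 360 patients: power 0.812 each; 2 × 0.812 × 0.188 = 30.5%.
- 400 patients: power 0.854 each; 2 × 0.854 × 0.146 = 24.9%.

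Cox, the method planned for subgroups. The hazard ratio implied by the risks is ln(0.88)/ln(0.70) = 0.358, and the pooled event rate is (30% + 12%)/2 = 21%. Schoenfeld power is Φ(√D/2 × |ln HR| − 1.96), with D the events in the subgroup. At 50:50:
- 360 patients: D = 37.8, power 0.884; 2 × 0.884 × 0.116 = 20.5%.
- 400 patients: D = 42, power 0.914; 2 × 0.914 × 0.086 = 15.7%.

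A simulation of Cox score and Wald tests (8,000 runs per size; exponential event times and fixed follow-up are assumptions) gives somewhat higher values: about 24–25% with 360 and 20–21% with 400. The Cox range at 50:50 is therefore about 16–25%.

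**Unequal splits, 360 patients.**

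| Split | Cox (Schoenfeld) | Fisher |
|---|---|---|
| 60:40 | 23.6% | 33.9% |
| 70:30 | 32.9% | 45.9% |
| 80:20 | 48.7% | 62.0% |
| 90:10 | 70.4% | 82.6% |

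**Three equal LMWH levels.** The chance of a mixed result is 1 − P³ − (1−P)³.
- Cox (Schoenfeld), 360 patients: D = 25.2, P = 0.731, giving 1 − 0.391 − 0.019 = 59%. The simulation gives 63–66%.
- Fisher: P = 0.605 with 360 and 0.673 with 400, giving 71.7% and 66.1%.

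**Smaller effect (30% versus 18%), 50:50, Fisher.** Power is 0.406 (360) or 0.448 (400), so exactly one subgroup is significant in 48–49%.

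**Interaction test.** With no true difference, the false-signal rate is 5% by construction. A simulated Wald test on the log odds ratio gave 4.5%. Its power is low:
- Ratio of hazard ratios, 50:50: SE = √(2 × 4/D), with D per subgroup, is 0.460 (360) or 0.436 (400). For 80% power the ratio must be exp(−2.80 × SE) = 0.28 or 0.29.
- Ratio of relative risks, 90 per arm in each half: SE(log RR) = √(1/27 − 1/90 + 1/10.8 − 1/90) = 0.328. The SE of the difference is 0.328 × √2 = 0.463. The 95% CI is ×/÷ exp(1.96 × 0.463) = 2.5, and 80% power needs a ratio of exp(2.80 × 0.463) = 3.7.

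**The case against.** A reader might infer that the plan powers all eight factors separately. It does not: the wording about separate analyses concerns LMWH start only. For the other factors the plan is silent, and a Cox model could carry an interaction term.

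A reader might also infer that the plan commits itself to reporting that IPC works in one subgroup and fails in another. It states no rule for declaring success in a subgroup and makes no claim of differing effects. The error arises only if separate results are compared, although powering the LMWH subgroups for separate analysis invites that reading.

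The warning about reproducibility does temper firm subgroup claims. It concerns multiplicity, however, and supplies no between-subgroup comparison.

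Sizing on Fisher and analysing by Cox is not a fault in itself. Under the stated assumptions Cox has at least comparable power, so the Fisher percentages overstate the problem for the planned method. Moving the subgroups to risk ratios would be a preference, not a correction.

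Finally, an interaction test at this size detects only very large differences, and making it the basis for claims weakens the stated reason for doubling. Both points stand. They argue for describing honestly what the doubled sample can show, not for leaving the comparison out.

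**Conclusion.** The point holds in limited form. Section 8 plans subgroup Cox models for eight factors and sizes one of them for separate analysis, but offers no test of whether the IPC effect differs. With the plan's own effect the same in both LMWH subgroups, exactly one would be significant in about 16–25% of trials by Cox (25–30% by Fisher), against about 5% false signals from an interaction test.

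Those figures assume a 50:50 split, which is the most favourable case. Unequal splits raise them, as do the three LMWH levels in the analysis text, where the sample size text has two. Subgroup shares are not in the documents, so the figures are a range and not a prediction. Only secondary analyses are affected; the primary comparison and its sample size stand.

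**What to change.** In the SAP text of section 8:
- For each factor defined in both arms, fit one Cox model with arm, factor and arm-by-factor interaction. Report the interaction p-value and the ratio of hazard ratios with its 95% CI.
- Show the subgroup hazard ratios with CIs as descriptive, and claim a difference in effect only from the interaction.
- Exempt the factor on whether IPC began before or after surgery. Control patients receive no IPC, so the interaction cannot be estimated; report this factor descriptively.

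In the sample size paragraph, say that the doubled sample gives precision within the LMWH subgroups but low power for interaction. At 50:50, 80% power needs about a 3.7-fold ratio of relative risks, or a ratio of hazard ratios of about 0.28–0.29. Add that a non-significant interaction does not show equal effects. Use the same LMWH-start levels in both paragraphs.

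The cost is wording and a few model terms on data already planned, with no new patients or procedures. The stated rationale for doubling has to be reworded, and subgroup statements become less definite.

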different IPC manufactures (with various pumps and sleeves) according to the clinical efficacy, compliance, patient's and nurse's satisfaction. The authors found some significant differences in the incidence of DVT, which ranged from 2.0% to 9.8% among the devices ( $p = 0.003$ ), and the best figures were observed for graduated sequential compression devices (SCD): 2.5% and 2.0% respectively. However, taking into account compliance and patient's and nurse's satisfaction, the best scores were demonstrated for the tight-length intermitted compression, which was associated with a DVT rate of 3.2%.

So, the second critical concern is compliance with IPC. Usually, compliance is far from 100% and typically ranges between 48 and 53%. It seems that compliance is higher in the intensive care unit (ICU) than in the profile surgical department. The main disadvantages of the IPC devices are related to their cumbersome size and their requirement to be connected to a static power source, both of which tended to confine patients to bed and delayed hospital discharge and rehabilitation. The studies that have aimed to assess compliance with IPC report that there might be a lack of device application as well as device functions. One study found that of all IPC devices that were applied, in 16% the pump did not function during the investigator's control visits.

The third point is that the minimal time of IPC application is unclear. Various studies have reported different durations of IPC application per day (14–20 h) depending on the type of device (portable or stationary). Another trial found that IPC in addition to pharmacoprophylaxis after orthopedic procedures was effective when applied for 6 h or more. However, the usual recommendation is to achieve 18 h of daily compliance.

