### **Secondary objectives:**

- To study the effect of IPC on the asymptomatic venous thrombosis occurrence during inpatient treatment in prespecified groups of patients:
  - Surgical profile,
  - Type of surgery,
  - The urgency of surgery,
  - The radicalism of surgery,
  - Type of anesthesia,
  - Malignant or benign disorder;
  - Preoperative, postoperative or delayed start of LMWH injections,
  - Pre-operative or post-operative IPC application,
- To study the effect of IPC on the isolated calf muscle DVT occurrence during inpatient treatment;
- To study the effect of IPC on the proximal DVT occurrence during inpatient treatment;
- To study the effect of IPC on the symptomatic PE occurrence during inpatient treatment;
- To study the effect of IPC on the fatal PE occurrence during inpatient treatment,

- To study the effect of IPC on the total VTE events that occur during inpatient treatment,
- To study the effect of IPC on the leg skin injury occurrence during inpatient treatment;
- To study the effect of IPC on the major and clinically relevant non-major bleeding occurrence during inpatient treatment;
- To study the compliance with IPC applied in the suggested regimen-required night free-of-compression interval;
- To study the effect of IPC on the symptomatic and asymptomatic venous thrombosis of lower limbs, symptomatic pulmonary embolism occurrence, and VTE related and VTE-non-related mortality during outpatient treatment and rehabilitation 30 and 180 days after surgery.

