### 3. Design

A two-center, prospective, randomized (with independent allocation), open-label clinical trial with a blinded assessor for efficacy outcomes, enrolling patients at extremely high risk for postoperative VTE (Caprini score of 11 and more). The patients should be randomly allocated into two groups (experimental [IPC] group and control group) according to the VTE prophylaxis they received. Both groups will receive anti-embolic stockings and injections of LMWH, and patients in the IPC group additionally will receive IPC. The total duration of prophylaxis should amount of 1 month, and patients will be followed-up for 6 months with regular clinical examination and duplex ultrasound scans. Figure 1 represents the global design of the study.

[figure not shown]

**Figure 1.** The global design of the study.

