#### **4.3. Sequential pneumatic compression**

Intermitted pneumatic compression should be applied with Cardinal Health™ Kendall SCD™ 700 Series Controller and Kendall SCD™ thigh-length Comfort Sleeves. The pumps will be provided by the Sponsor (10 pumps by Cardinal Health™), and the sleeves will be purchased by the Clinical centers. Sleeves should be fitted according to the manufacturer's instructions and used in a disposable manner. Sleeves should be changed when they become soiled or lost their fixation.

IPC should be started just before the surgery in the operating room during general anesthesia induction or after regional anesthesia application before covering the operating field with the sterile material. Also, it is allowed to apply IPC within 12 h after surgery. The main conditions of IPC application are as follows: no venous thrombosis

confirmed by DUS, no skin lesions on the leg, no signs of skin and soft tissue infections of the legs, ABI >0.6.

IPC should be applied around-the-clock in the ICU, and at the time of bed-rest with a 6 h free-of-compression interval from 0 am to 6 am in the profile surgical department. The IPC required to be used during the whole inpatient treatment period.

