#### **5.4. Examination during inpatient treatment**

The following data on surgical procedure should be obtained from the medical records after intervention: the surgical profile (e.g., abdominal, thoracic, neck, pelvis, cranial), type of surgery (open, endoscopic, endoscopy assisted), urgency of surgery (emergent = performed in 0–2 h after admission, urgent = performed in 0–6 days after admission, elective = performed independently at the time of admission), radicalism of surgery (radical, palliative), type of anesthesia (general, regional, combined), surgery duration, blood loss, and intraoperative infusion.

The routine clinical examination of the patient will be performed in a daily manner with special attention to the possible complications, such as DVT, SVT, PE, bleeding, and leg skin injury. IPC sleeves should be removed for 15–20 mins every day for skin inspection and investigation of pedal pulsation. Consultation of any relevant specialist

(cardiologist, neurologist, pulmonologist, infections) should be performed if any complication or development of new co-morbidity will be observed during the follow-up.

DUS should be performed every 3–5 days after surgery and in emergency manner if any clinical suspicion for DVT or SVT appeared. In an emergency manner, DUS may be performed by a blinded expert or specialist on duty on weekend and holidays. However, all conclusions of non-investigational medical staff must be verified by a blinded expert.

SPECT/CT or CTPA should be used to verify PE in an emergency manner if clinical suspicion appeared. An autopsy must be performed in all died patients to verify the absence of DVT and PE.

In case of any clinical suspicion for a VTE event, IPC should be interrupted until final verification of the diagnosis. In the case of positive DUS, CTPA, and SPECT/CT, the therapeutic anticoagulation should be prescribed, and IPC should be removed. In the case of clinical suspicion for VTE with negative results of instrumental tests, IPC should not be returned until the proper diagnosis that mimics VTE will be found.

Any revealed leg skin lesion should be judged individually for the possibility to continue ECS and IPC application. If the decision will be made to stop IPC, the patient should be withdrawn from the study according to the protocol.

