### 5.6. Compliance measure

No specific compliance measures are designed for the use of ECS and LMWH injections. The compliance with the IPC device will be measured as follows. Every day, the investigator (weekdays) or surgeon on duty (weekends and holidays) should visit a patient five times and check that, if the subject is confined to bed, the sleeves are applied to his legs and that the pump is functioning. The results of such visits should be registered in a specifically designed compliance sheet (Fig. 4). The compliance will be calculated as a proportion of all marks testified that IPC was applied to the total number of visits that found patient in the bed.

		Visit 1	Visit 2	Visit 3	Visit 4	Visit 5	Compliance
Day X	Patient is in bed	√	√	√	√	√	100%
	IPC is turned on	√	√	√	√	√	
Day Y	Patient is in bed	√	-	-	-	√	100%
	IPC is turned on	√	-	-	-	√	
Day Z	Patient is in bed	√	√	√	√	√	40%
	IPC is turned on	√				√	

**Figure 4.** An example compliance sheet, which assessed compliance with IPC. The right column represents the result of the calculations.

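### Section 8: the 90% IPC-compliance restriction selects patients in one arm only, and the pre-/post-operative IPC subgroup contains no control patients

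*Combined protocol and SAP*

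**What the plan says.** Section 3 (Design) gives stockings and LMWH to both groups and adds that "patients in the IPC group additionally will receive IPC". Section 4 likewise assigns the device to the experimental group only.

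Section 5.6 defines IPC compliance as a "proportion of all marks testified that IPC was applied to the total number of visits that found patient in the bed". It states that no compliance measure is designed for stockings or LMWH.

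Section 8 then plans two analyses on IPC-specific variables:

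- a sensitivity analysis on "compliance with IPC (restricted for 90% and more"), with no statement of how control patients are handled or which test is used;
- Cox models for prespecified subgroups, including "pre-operative or post-operative IPC application". The secondary objectives in section 2 list "Pre-operative or post-operative IPC application" among the patient groups in which the effect of IPC is to be studied.

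Section 8 also restricts sensitivity analyses to follow-up of 7 days or more and to two or more postoperative duplex scans. It does not define either count.

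**The concern.** Compliance arises after allocation and exists in one arm. A 90% threshold can remove IPC patients but no controls, so the randomised comparison is lost on one side. If compliers differ in risk from non-compliers, the restricted result moves even when IPC does nothing. A reader who takes it as a sensitivity analysis may see confirmation or contradiction of the primary result where there is neither.

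The IPC-start subgroup has a more basic fault. Controls have no IPC start, so neither level contains a comparator, and the stated objective (the effect of IPC within each group) cannot be met.

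**Working it through.** **Plan's own figure.** Section 8 assumes 30% versus 12%, two-sided alpha 0.05 and 80% power, and gives 90 per arm. The continuity-corrected two-proportion formula returns 90 per arm, and exact enumeration of the two-sided Fisher test at 90 per arm gives 81.2% power. Then 180/0.9 = 200, doubled to 400, or 200 per arm at equal allocation. The sample size is reproduced and is not in dispute.

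**1. Compliance restriction**

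From section 8: control risk 30%, IPC risk 12% under the planned effect, 200 per arm. The documents give neither the share of IPC patients who will reach 90% compliance nor the risk by compliance, so these are assumptions:

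- s = share of the IPC arm at 90% compliance or more: 0.5 or 0.9;
- k = non-complier risk divided by complier risk: 1.5 or 2, and the reverse, 1/1.5 or 1/2.

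The whole IPC arm has risk p = s·pc + (1 − s)·k·pc, so the complier risk is pc = p / [s + (1 − s)k]. The apparent relative risk is RR = pc / 0.30, because all controls stay in. Rejection is by exact enumeration of the two-sided Fisher test at 0.05, with 200s IPC patients against 200 controls. Section 8 names no test for this analysis; Fisher is used because it is the primary test.

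No true effect, p = 0.30. Example, s = 0.5 and k = 2: pc = 0.30 / (0.5 + 0.5 × 2) = 0.20, RR = 0.20/0.30 = 0.67.

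| s | k | Complier risk | Apparent RR | Fisher rejection |
|---|---|---|---|---|
| 0.5 | 1 (no selection) | 30.0% | 1.00 | 4.3% |
| 0.5 | 1.5 | 24.0% | 0.80 | 17.2% |
| 0.5 | 2 | 20.0% | 0.67 | 43.5% |
| 0.5 | 1/1.5 | 36.0% | 1.20 | 16.3% |
| 0.5 | 1/2 | 40.0% | 1.33 | 37.2% |
| 0.9 | 1 (no selection) | 30.0% | 1.00 | 4.4% |
| 0.9 | 1.5 | 28.6% | 0.95 | 5.4% |
| 0.9 | 2 | 27.3% | 0.91 | 8.1% |
| 0.9 | 1/1.5 | 31.0% | 1.03 | 4.9% |
| 0.9 | 1/2 | 31.6% | 1.05 | 5.6% |

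With 180 evaluable per arm instead of 200, the rows for k = 1.5 and 2 give 16.3% and 40.4% (s = 0.5) and 5.2% and 7.5% (s = 0.9), so the pattern does not depend on that choice.

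Under the planned effect, p = 0.12 and the true RR is 0.40. With s = 0.5 the same formula gives 0.32 or 0.27 for k = 1.5 or 2, and 0.48 or 0.53 in the reverse direction.

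The documents do not settle the direction. Compliers may be lower-risk patients. Equally, section 1 says "It seems that compliance is higher in the intensive care unit (ICU) than in the profile surgical department" and section 4.3 says "IPC should be applied around-the-clock in the ICU", so compliers may be the sicker ones.

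**2. IPC-start subgroup**

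Sections 3 and 4 give IPC to one arm. Pre-operative and post-operative start are therefore levels within that arm, each with zero controls, and no IPC-versus-control hazard ratio exists within a level.

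Each level can be set against all controls, but that contrast is confounded by whatever determines the start. Assume no true effect, 50% or 70% of IPC patients starting pre-operatively, and post-operative starters at r = 1.5 or 2 times the risk. Pre-operative risk is 0.30 / [share + (1 − share)r]; post-operative risk is r times that. The RRs against all controls are 0.67 to 0.87 for pre-operative start and 1.20 to 1.54 for post-operative start: an apparent subgroup difference with no effect of IPC at all.

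**The case against.** **The bias may be small.** Section 5.6 counts only visits that find the patient in bed, and the night-free interval is meant to raise compliance, so a large share may reach 90%. The 48% to 53% in section 1 is compliance in earlier reports, not the share reaching 90%. This stands as to size: the rows at s = 0.9 show little distortion. It does not make the comparison like-for-like.

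**Each IPC-start level can be compared with all controls.** It can, and section 8 says only that Cox models will be used. But that is a confounded contrast and not a subgroup effect of IPC, which is what section 2 asks for.

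**These are supportive analyses.** True: the primary Fisher test is untouched, and section 8 already cautions about its unadjusted intervals.

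Four stronger readings are tempting, and the documents do not support them:

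- *The restriction flatters IPC, or can never be informative.* The direction is open, and there is no bias if compliance and risk are unrelated.
- *VTE itself lowers measured compliance.* Section 5.4 does say "IPC should be interrupted until final verification of the diagnosis", but this follows clinical suspicion, whereas the primary endpoint is asymptomatic thrombosis found by scan, and section 3.3 makes any VTE event a withdrawal criterion. Little of this route remains.
- *The 7-day and two-scan restrictions delete early events.* That holds only if follow-up and scan counts end at VTE, which section 8 does not say.
- *An unaffected primary test clears the exclusions in sections 3.4 and 4.2.* It does not; their fit with intention-to-treat is a separate question.

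**Conclusion.** Both analyses are wrong as written, and this follows from the text alone: the compliance restriction acts on one arm, and the IPC-start subgroup has no controls.

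The size of the first problem is assumption-dependent. With no true effect, it runs from an apparent RR of 0.67 to 1.33 with 16% to 43% rejection (half the arm compliant) down to 0.91 to 1.05 with 5% to 8% rejection (90% compliant), against about 4% without selection. These figures rest on the assumed 1.5- or 2-fold risk ratios. The second problem has no size: the planned hazard ratios cannot be estimated.

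The plan should be amended, but neither fault touches the primary Fisher test or the sample size.

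**What to change.** Change the wording of section 8, and of the matching secondary objective in section 2:

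- Do not use the 90% restriction as a between-arm robustness check. Report compliance, and outcome by compliance, descriptively within the IPC arm.
- Remove IPC start from the between-arm subgroup list and report it descriptively within the IPC arm. If a timing subgroup is wanted, use a variable known in both arms at randomisation, such as enrolment before or after surgery (section 3.2).
- For the 7-day and two-scan restrictions, state whether follow-up and scan counts end at VTE. Do not keep every event while applying the minimum only to event-free patients, because that selects on the outcome. With equal 30% risk, a rate becomes 0.30 / [0.30 + 0.70(1 − g)] when a share g of event-free patients is removed: 32.3% at g = 0.1 and 38.0% at g = 0.3. Unequal removal would thus give an RR of 0.85 or 1.18 with no true effect.

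The cost is one sensitivity analysis and one between-arm subgroup, neither of which has a matching control group as written.

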### **3.5. Endpoints and definitions**

**Primary endpoint:** asymptomatic venous thrombosis of the lower limbs detected by DUS during inpatient treatment.

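### Section 8 expects no missing primary-endpoint data and plans no analysis of it, although the plan's own loss allowance and withdrawal rules provide for such data

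*Combined protocol and SAP*

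**What the plan says.** All references are to the combined protocol and SAP.

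- **Endpoint and test.** Section 3.5 defines the primary endpoint as "asymptomatic venous thrombosis of the lower limbs detected by DUS during inpatient treatment". Section 5.4 schedules scans every 3–5 days after surgery. Section 8 states: "The primary statistical analysis is designed as intention-to-treat with the use of two-tailed Fisher's exact test".
- **Missing data.** Section 8: "Missing data on the primary endpoint are not anticipated in the inpatient settings, so no analysis for missing data being planned". It adds that "imputation for missing values will not be performed".
- **Sample size.** Section 8 starts from 180 evaluable patients and allows 10% for deviations, patient decision "or incomplete data, the sample size is calculated as 200 subjects". It then doubles the number to support separate analyses by early or delayed start of LMWH.
- **Withdrawal.** Section 3.3 withdraws patients for, among other reasons, leg skin injury, conditions that end IPC or ECS use, bleeding or other conditions that end LMWH, and changed prophylaxis. Section 5.4, on skin lesions: "If the decision will be made to stop IPC, the patient should be withdrawn from the study according to the protocol".
- **Exclusion from analysis.** Section 3.4 removes from the final analysis patients who missed two or more scheduled scans or the last one before discharge, and those with no IPC compliance record. Section 4.2 removes patients with no enoxaparin after 5 days.
- **Supportive analyses.** Section 8 plans a per-protocol analysis and restrictions to IPC compliance of 90% or more, follow-up of 7 days or more, and two or more postoperative scans.

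**The concern.** An asymptomatic thrombosis is known only if a scan is done, so a patient who leaves the scan schedule without an event has an unknown primary outcome. The statement that this will not happen is the only reason given for planning nothing, and the sample size paragraph and sections 3.3, 3.4 and 5.4 contradict it.

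The documents do not say whether scheduled scans continue after withdrawal. Nor do they say how a withdrawn patient enters the primary test. Section 3.4 would drop a patient without the required scans; intention-to-treat would keep that patient, presumably as event-free. These two routes behave differently.

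Loss may also be uneven. Stopping IPC can trigger withdrawal only in the IPC arm, and an empty IPC compliance sheet can lead to exclusion only there. If more IPC patients are lost and they are scored as event-free, the IPC event rate falls without any effect of IPC. The trial is open-label, so a rule chosen after seeing who withdrew would carry little weight.

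**Working it through.** **1. Is the 10% allowance part of the primary-endpoint calculation?** Inputs from section 8: control rate 30% ("standard prophylaxis with ECS and LMWH was assumed as 30", in per cent); "the absolute difference of 18% is assumed", hence 12% with IPC; two-sided 5% level; 80% power.

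- Without continuity correction: n = [1.960·√(2·0.21·0.79) + 0.842·√(0.30·0.70 + 0.12·0.88)]² / 0.18² = 79.2, so 80 per group.
- With correction: n′ = (79.2/4)·[1 + √(1 + 4/(79.2·0.18))]² = 90 per group, as stated. Exact Fisher power at 90 per group is 81.2%.
- Loss: 180/(1 − 0.10) = 200, as stated. Doubled, this is 400, of whom 10% is 40.

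So the allowance is a working part of the calculation for the same inpatient endpoint. Power is not the problem: with 180 evaluable per arm, exact Fisher power is 98.6%.

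**2. False-positive rate under different handling.** Assumptions: 200 per arm, true rate 30% in both arms, loss unrelated to outcome and before any event is detected. If unobserved counts as no event, the apparent rate is 0.30 × (1 − fraction lost). Rejection rates of the two-sided Fisher test are by full enumeration.

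| Loss (IPC / control) | Handling | Apparent rates | Rejection |
|---|---|---|---|
| none | – | 0.300 / 0.300 | 3.9% |
| 10% / 0% | no event | 0.270 / 0.300 | 8.4% |
| 15% / 5% | no event | 0.255 / 0.285 | 8.5% |
| 5% / 0% | no event | 0.285 / 0.300 | 5.0% |
| 12% / 8% | no event | 0.264 / 0.276 | 4.6% |
| 10% / 10% | no event | 0.270 / 0.270 | 3.9% |
| 10% / 0% | dropped (180 vs 200) | 0.300 / 0.300 | 4.4% |

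In the second row the apparent relative risk is 0.270/0.300 = 0.90, and 8.1% of trials reject in favour of IPC, against 2.0% with no loss.

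**3. Robustness at the planned effect.** Assumptions: 20 missing per arm, planned rates among those observed (22/180 IPC, 54/180 control).

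- Complete cases: RR 0.41 (95% CI 0.26–0.64), p = 0.00005.
- Missing as no event, 22/200 vs 54/200: RR 0.41, p = 0.00006.
- Missing at 30% in both arms, 28/200 vs 60/200: RR 0.47 (0.31–0.70), p = 0.0002.
- Tipping point: 15 of 20 missing IPC patients with events and no missing control with one, 37/200 vs 54/200: p = 0.056.
- Worst case, 42/200 vs 54/200: RR 0.78 (0.55–1.11), p = 0.20.

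**4. Where it is more fragile.**

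- *LMWH subgroup.* If the subgroups are of equal size (assumed), each has 100 per arm. With 10 missing per arm and 11/90 vs 27/90 observed, 4 of 10 missing IPC patients with events and no missing control with one gives 15/100 vs 27/100, p = 0.055.
- *Smaller effect.* With 36/180 vs 54/180 observed (illustrative, chosen near the threshold), p = 0.038 for complete cases and 0.041 with missing as no event. With 6 of 20 events among the missing in each arm, 42/200 vs 60/200, p = 0.051. RR moves only from 0.67 to 0.70.

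**The case against.** Four stronger readings are tempting, and the documents do not support them.

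- **That withdrawal ends scanning.** Sections 3.3 and 5.4 say the patient is withdrawn from the study; neither says inpatient scans stop. Some of section 8 points the other way: the Cox censoring rule lists VTE, death and discharge but not withdrawal. The per-protocol set excludes patients who discontinued a component, which presupposes that they remain in the intention-to-treat set. What stands is that the plan is silent.
- **That the plan contains no check.** It has four restricted analyses, and those requiring 7 days of follow-up or two scans would remove many patients lost early. But each keeps only the more complete patients; none asks what follows if the unobserved had events.
- **That the false-positive rate doubles.** This needs markedly unequal loss together with scoring the lost as event-free. Section 3.4 would drop a patient without the required scans instead, and under the same assumptions dropping gives 4.4%. Bleeding, LMWH, ECS and refusal triggers apply to both arms, so strong imbalance cannot be presumed.
- **That the main conclusion is unsafe.** At the planned effect it takes an extreme pattern to lose significance.

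It is also fair that the 10% pools deviations, patient decision and incomplete data, so it is an upper figure for outcomes that are truly missing. None of this removes the contradiction within section 8 or supplies the missing handling rule.

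**Conclusion.** The point holds as a gap that should be closed. The premise for planning no missing-data analysis conflicts with the plan's own 10% allowance and its scan and withdrawal rules. The handling of withdrawn, unscanned patients is undefined, and section 3.4's exclusions conflict with the intention-to-treat set.

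The consequence depends on facts the documents do not give: how many outcomes are missing, in which arm, and how they are scored. On the stated assumptions the false-positive rate runs from 3.9% (equal loss) to about 8.5% (a 10-point imbalance scored as no event). A result at the planned effect would survive all but strongly arm-dependent missingness; a smaller effect, or an LMWH subgroup, might not.

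**What to change.** - Delete the sentence saying that missing primary data are not expected, and reconcile section 8's missing-data text with its sample size paragraph and with sections 3.3 and 3.4.
- State that withdrawn patients stay in the intention-to-treat set, and that results of the inpatient scans already scheduled are collected to discharge unless consent is withdrawn.
- Define the primary outcome as missing when no event has been found and the scans fail section 3.4's own criteria (two or more missed, or the final one missed). A patient with one missed scan and a negative final scan then still counts as observed.
- Report missingness by arm and reason.
- Add one supportive tipping-point or extreme-case analysis of the intention-to-treat Fisher comparison. Multiple imputation is optional.

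The cost is SAP wording and modest analysis work, with no added patients and no change to the primary test. The downside is that the result may look less firm if missingness turns out unequal.
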